Acute alcohol is associated with increased cerebral blood flow (CBF). It is unknown if changes in CBF are due to alcohol, acetate, or both. Determining the differential effects of alcohol and acetate on brain function is significant as it could lead to new treatments targeting alcohol metabolites. The goal of the proposed study is to determine feasibility of measuring effects of oral alcohol and intravenous acetate on cerebral blood flow and function in moderate drinkers with the objective to use the data collected for an R01 or R21 application. Although currently there is no data in the literature on this, finding such changes would be important and could direct future prevention and treatment plans for alcohol use disorders. For this feasibility pilot study we propose to investigate the effects of acetate and alcohol on CBF and brain function with two specific aims.

Aim 1. Investigate the effects of acetate on cerebral blood flow and function in controls and AUD individuals

Preliminary data will be collected for the hypothesis that compared to placebo given IV acetate given IV will: a) increase CBF as measured by arterial spin labeling (ASL); and b) decrease blood oxygen level dependent (BOLD) activity during functional magnetic resonance imaging (fMRI); and c) these changes will be greater in AUD individuals than controls

Aim 2. Investigate the effects of alcohol on cerebral blood flow and function in controls and AUD individuals

Preliminary data will be collected for the hypothesis that compared to non-alcoholic jello shots, orally ingested alcohol jello shots will: a) increase CBF, and b) decrease BOLD activity; and c) these changes will be greater in AUD individuals than controls.

II. Background and Significance:

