Exclusions-all: Participants will be excluded if they: (1) have a “facial flushing” response to alcohol; (2) are pregnant or nursing; (3) have major medical problems including diabetes, uncontrolled high blood pressure (> 150/90), prior neurological or psychiatric history (schizophrenia, bipolar, or current major depressive disorder, epilepsy (alcohol withdrawal seizures is not an exclusion)); (4) have ever been told they have or been diagnosed with liver or kidney disease; (5) have a diagnosis of chronic gastrointestinal disease; (6) are obese (BMI>30 kg/m²); (7) have prior head trauma resulting in loss of consciousness>15 min.; (8) have MR exclusions which include claustrophobia, intracranial, orbital, or spinal metal, pacemakers, cochlear implants, cardiac stents or other non-MR-compatible implants or devices.

C. Study Design and Research Methods

Study Design

This is a pilot study to determine the feasibility of measuring effects of acetate alone and acetate obtained as a byproduct of alcohol metabolism on CBF and brain activity. Our recruitment goal will be 50 subjects: 40 healthy controls who are social drinkers (1-14 drinks per week) to achieve a target of n=20 scanned for Aim 1 and n=20 scanned for Aim 2, with a final usable healthy control target of n=15 for Aim 1 and n=15 for Aim 2 (a few subjects may not qualify for data analysis due to excessive head motion in scanner); and 10 AUD individuals, to achieve a target of n=7 scanned for Aim 1. AUD participants seeking treatment will be excluded from Aim 2 (alcohol arm). Moderate drinkers will be recruited through advertisements and flyers. AUD subjects will be recruited from the Center for Dependency, Addiction and Rehabilitation (CeDAR) at the University of Colorado Anschutz Medical Campus.

Order effects: Before the study commences, test-retest reliability will be conducted on two healthy controls on MR measures by scanning them twice in a single day, with no intervention. The null hypothesis of no difference in brain activity and CBF will be tested, between the two sessions. Notably, the literature shows high reliability for test-retest of CBF using ASL at various time intervals (Floyd et al, 2001, Chen et al., 2011).

Session 1: Consent and diagnostic assessment (total time ~1 hour)

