Power and Confidence Interval Width: This study is a pilot study, designed to estimate the size of the effect, and provide accurate parameter estimates for a later, more definitive study. The power analysis here is based on the work of Schwartz et al. (Schwartz et al., 1993), who studied CBF before and after drinking and observed a mean difference in flow measured as a ratio of cortex/cerebellum (after – before) of 0.054 with standard deviation of the difference of 0.085. The smallest difference in CBF that a study with 10 people can detect using repeated measures ANCOVA with 90% power and a Type 1 error of 0.05 is a difference of 0.09 (ratio of cortex/cerebellum). Therefore we should have adequate power to detect a difference with alcohol. There is no prior CBF data on acetate in the literature to perform power analysis for acetate. This study is designed to provide preliminary data for a later study and an estimation of the N necessary for that study to provide sufficient power for analysis.

G. Summarize Knowledge to be Gained:

This proposal is relevant to public health because of the considerable impact alcohol has on the health of individuals and in terms of legal, medical, and social costs to the country. Again, this is a pilot study to determine the feasibility of measuring effects of oral alcohol and intravenous acetate on CBF and function in moderate drinkers and AUD individuals. Data from this study will be used to apply for funds to conduct a larger study. The results from this the later,

larger project will add to our knowledge about mechanisms of acute alcohol's effects on brain function and the role of acetate in these effects.

H. References:

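### The detectable difference of 0.09 at n=10 is slightly optimistic for the usual two-sided test; without further assumptions it is about 0.098

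*Combined protocol and SAP*

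**What the plan says.** The power paragraph in section IV.F takes its inputs from an earlier study of CBF before and after drinking: a mean change of 0.054 in the cortex-to-cerebellum ratio, with a standard deviation of the difference of 0.085. It continues that the smallest CBF difference a study of ten people "can detect using repeated measures ANCOVA with 90% power and a Type 1 error of 0.05 is a difference of 0.09". This is the only detectable-difference figure in the plan.

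The error rate is given as "a Type 1 error of 0.05" without saying whether it is one- or two-sided, and no other section says so. The aims are directional: for acetate, CBF is expected to "increase CBF as measured by arterial spin labeling (ASL)"; for alcohol, "orally ingested alcohol jello shots will: a) increase CBF". The order-effects paragraph in section IV.C is non-directional: "The null hypothesis of no difference in brain activity and CBF will be tested, between the two sessions".

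Two analyses of CBF are described in section IV.F. The pilot's region-of-interest analysis is a paired t-test, run separately for acetate and for alcohol. The whole-brain analysis is a repeated measures ANCOVA with drug as the within-subject factor, adjusted for age and monthly drinks. Section IV.C sets a usable target of 15 healthy controls for each aim.

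**The concern.** A drug-versus-placebo main effect with two levels is tested by an F statistic with one numerator degree of freedom. That F is the square of a t statistic, so the test rejects for a change in either direction. A reader who takes the named method at face value will compute a two-sided power figure, and from the stated inputs will not obtain 0.09 at n=10.

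What is at stake is modest. The figure does not set the sample size. However, the pilot is meant to supply the inputs and the method for sizing a later study, and a figure whose sidedness, error degrees of freedom and covariate assumption are all unstated is a poor template for that.

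**Working it through.** **Inputs.** From section IV.F: standard deviation of the difference 0.085, n=10, alpha 0.05, power 90%. From section IV.C: usable n=15 per aim. Assumption for the main check: covariates explain none of the variance of the difference.

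**Standard error at n=10.** 0.085/√10 = 0.02688.

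**Reproducing the plan's figure.** The two-sided normal approximation gives (1.960 + 1.282) × 0.02688 = 0.0871, which rounds to 0.09. Solved for n, it gives (3.242 × 0.085/0.09)² = 9.4, rounded up to 10. This may be the route that was taken, but the plan shows no formula. The one-sided normal version gives 0.079 and does not match. A one-sided exact t-test also matches: 0.0854 on 9 degrees of freedom, or 0.0877 on 7.

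**The usual two-sided test, exact.** With the noncentral t distribution on 9 degrees of freedom, 90% power requires a difference of 0.0981, which is 3.65 standard errors (0.0981/0.02688). At 0.09 the noncentrality is 0.09/0.02688 = 3.35 and the power is 84.5%.

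| Calculation at n=10, SD 0.085 | Detectable difference at 90% power | Power at 0.09 |
|---|---|---|
| Normal, one-sided | 0.079 | 95.6% |
| Normal, two-sided | 0.087 | 91.7% |
| Exact t, one-sided, 9 df | 0.085 | 92.5% |
| Exact t, two-sided, 9 df | 0.098 | 84.5% |

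In sample size terms, a two-sided paired t-test has 88.5% power at 0.09 with 11 people and 91.5% with 12, so it needs 12 rather than 10.

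**What covariates could do.** If covariates cost degrees of freedom and explain nothing, the two-sided figure is 0.0998 on 8 degrees of freedom (one covariate) or 0.1020 on 7 (two). If they explain a share R² of the variance of the difference, these values are multiplied by √(1 − R²). The R² needed is then:

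- to reach 0.09 exactly: 1 − (0.09/0.0998)² = 19% with one covariate; 1 − (0.09/0.1020)² = 22% with two;
- to fall to 0.095, below which the figure rounds to 0.09: 1 − (0.095/0.0998)² = 9% with one; 1 − (0.095/0.1020)² = 13% with two.

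The documents give no R², so these are ranges, not estimates.

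**At the planned usable size.** For n=15 the standard error is 0.085/√15 = 0.02195. The two-sided paired t-test detects 0.0766 with 90% power, and its power at 0.09 is 96.8%.

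**The case against.** The strongest defence is that no error has been shown. The power paragraph does not declare a two-sided test, and its 0.09 follows from a standard textbook approximation or from a one-sided t-test, which the directional aims could motivate. Given to two decimals, 0.09 also fits a two-sided ANCOVA whose covariates explain a plausible share of the variance. This stands, and it rules out saying that the calculation is wrong. It does not make the figure reproducible: each of these routes needs an assumption that the reader is not given, and the normal approximation is inaccurate with 9 error degrees of freedom.

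A second defence is that the gap is immaterial. It is about 0.01 on the ratio scale, and at 15 usable controls the two-sided test exceeds 90% power for 0.09. This also stands, and it limits the point to a corrected number.

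A reader might infer more than the documents support in three ways:

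- **That the true ANCOVA figure is 0.102, with 82% power at 0.09.** This charges two degrees of freedom for covariates and credits them with no explained variance. The plan does not say that the power calculation used those covariates. Covariates that are constant within a person use within-person error degrees of freedom only if their interactions with treatment are fitted, which is not specified.
- **That the pilot is too small to detect 0.09.** The n=15 result contradicts this under the same inputs.
- **That unstated sidedness would change the trial's conclusions.** The stated aim is feasibility and estimation, and no decision rule depends on a borderline p-value.

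**Conclusion.** The stated 0.09 at n=10 is optimistic for the usual two-sided main-effect test. That test detects about 0.098 with 90% power and has about 85% power at 0.09. The conclusion rests on the plan's standard deviation of 0.085, 9 error degrees of freedom, and covariates that explain none of the variance of the difference. The plan's figure is recovered only under an assumption it does not state: a one-sided test, a two-sided normal approximation, or a covariate R² of roughly 9–13% (to round to 0.09) or 19–22% (to equal it).

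This is a small correction to a stated number. It does not show that the pilot is under-sized for a difference of 0.09. Whether 0.09 or any replacement supports the sentence claiming adequate power for alcohol, given the cited effect of 0.054, is a separate question that this point does not settle.

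**What to change.** In the power paragraph of section IV.F, replace 0.09 by the two-sided figure for the test and size the pilot will use: 0.077 with 90% power at the usable n=15, for the paired t-test in the region-of-interest plan. If n=10 is kept, give about 0.10. State that the test is two-sided at 0.05. If an ANCOVA figure is reported as well, give its error degrees of freedom and assumed R².

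The cost is one number and a sentence or two of wording. The n=10 figure becomes slightly less favourable; the design and sample size do not change.

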E. Potential Scientific Problems:

1. Sex effects: Alcohol metabolism differs in men and women and several studies find an interaction between sex and alcohol's effect on terms of brain morphometry (Hommer et al., 2001), function, and CBF (Marxen et al., 2014; Rickenbacher et al., 2011). It should be noted, however, that not all studies have confirmed sex differences in brain morphometry (Demirakca et al., 2011). There will not be power to detect sex effects. Our goal is to demonstrate feasibility.

2. Vasomotor effect: The BOLD signal reflects complex interactions between CBF, cerebral blood volume, and oxygenation. We plan to study differences in global and regional vascular effects in acetate vs. alcohol treatment. The fMRI BOLD measurements are insensitive to time lags or shifts in the hemodynamic response of the brain during decision-making. Therefore in exploratory studies a finite impulse response (FIR) model will be used, according to prior work (Yamamoto et al., 2014).

3. Diurnal variations: We cannot exclude the possibility of diurnal fluctuations confounding our findings. The alternative to conduct blinded placebo and treatment studies on two separate days in the same participant would be a hardship on participants.

4. Dose-response: A dose-response for acetate or alcohol will not be obtained. Fortunately, the pharmacokinetics of alcohol are well established and the timing of the MR scans is planned according to Figure 2. The pharmacokinetics of acetate are not as well established. The IV infusion protocol will give us better control of plasma levels, and serum acetate and alcohol will be assayed.

F. Data Analysis Plan:

Blood alcohol and acetate: Levels of blood alcohol and acetate will be analyzed using colorimetric enzyme-linked immunosorbent assays (ELISA).

MR measures: MR CBF and fMRI BOLD activity data will be processed in SPM12 (The FIL Methods Group, 2014). First, each participants' T1-weighted anatomic image will be skull-stripped then coregistered to the Montreal Neurological Institute (MNI) MNI152 template. The transformation matrix generated from this step will be applied to CBF and BOLD contrast maps of interest.

MR CBF: Motion-corrected ASL CBF images (mL/100g/min) will be generated by the scanner software. CBF maps will be skull-stripped and co-registered to each participant's T1-weighted anatomic image in native space followed by application of the transformation matrix to MNI space.

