BOLD fMRI pre-processing: After discarding the first 4 volumes for saturation effects, images will be corrected for movement with a 3-dimensional rigid body transformation. Participants with scan-to-scan head movement >2 mm will be excluded. Motion parameters will be modeled as nuisance variables. Images will be normalized to MNI space using the two step transformation procedure described for MR CBF. Images will be spatially smoothed with a 6 mm full-width-half-maximum isotropic Gaussian kernel, filtered to remove low-frequency fluctuations (128 s high pass filter), and corrected for temporal autocorrelation.

BOLD fMRI: Model specification and contrast of interest: The time series will be predicted by nine regressors, consisting of decision and outcome for each of the four decks, plus motor control. Motion parameters will be modeled as nuisance regressors. The stimulus function will be convolved with the canonical hemodynamic response function (HRF). We are primarily interested in effects of acetate or alcohol on brain activity during the decision phase of the task. The primary outcomes will be the contrast of Decision>motor control baseline and Outcome>motor control baseline. For each participant these contrast maps will be brought to the second level for subsequent ROI and whole-brain analyses.

Regions-of-interest (ROI): ROI and whole brain analyses will be conducted for outcome measures of CBF and fMRI BOLD activity. Six anatomically- defined ROIs will be based on the neural circuitry found to be involved during decision-making on the modified IGT and which overlap with brain regions showing altered signal after acute alcohol (Anderson et al., 2011; Bjork and Gilman, 2014). ROIs will be bilateral ventral striatum (VST), dorsal striatum, insula, and anterior cingulate cortex (ACC), orbitofrontal cortex (OFC), and dorsolateral prefrontal cortex (DLPFC). VST and DST will be manually drawn, based on published landmarks (Mawlawi et al., 2001). For the OFC, insula, ACC, and DLPFC, the automated anatomical labeling atlas (AAL) (Tzourio-Mazoyer et al., 2002) will be used. Figure 3 shows examples of VST=green, DST=orange, OFC=blue, insula=red.

[figure not shown]

Fig 3. Regions of interest

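### The CBF power figures are for a cortex/cerebellum ratio that no planned analysis uses, and the global vascular effects the plan mentions have no specified estimate

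*Combined protocol and SAP*

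**What the plan says.** **Benchmark.** Section IV.F, Power and Confidence Interval Width, takes its inputs from one earlier study of flow before and after drinking: a "mean difference in flow measured as a ratio of cortex/cerebellum (after – before) of 0.054", with a "standard deviation of the difference of 0.085". For 10 participants, at 90% power and a 5% Type I error under a repeated-measures ANCOVA, it states that the minimum detectable change "is a difference of 0.09 (ratio of cortex/cerebellum"). From this it concludes that power for alcohol is adequate. It adds that no prior CBF data exist for acetate.

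**What the trial measures.** Section IV.F, MR CBF: "Motion-corrected ASL CBF images (mL/100g/min) will be generated by the scanner software". The Regions-of-interest paragraph lists the regions: "ROIs will be bilateral ventral striatum (VST), dorsal striatum, insula, and anterior cingulate cortex (ACC), orbitofrontal cortex (OFC), and dorsolateral prefrontal cortex (DLPFC"). They were chosen for their role in the decision-making task.

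**How it is analysed.** In the pilot, the regional CBF values get paired t-tests, acetate and alcohol separately. The whole-brain analysis is a repeated-measures ANCOVA in SPM12 at p < 0.05 uncorrected.

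**Global effects.** Section IV.E, item 2 (Vasomotor effect): "We plan to study differences in global and regional vascular effects in acetate vs. alcohol treatment".

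**The concern.** The effect, SD and detectable difference all sit on a ratio scale, while the CBF tests sit on an absolute scale. A ratio to the cerebellum removes any change common to both regions; absolute regional flow keeps it. The two can move differently, so a power statement for one does not carry over to the other.

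Two things are at stake. First, the power section assures the reader of adequate power for a quantity the trial does not plan to compute. Second, Aims 1a and 2a hypothesise an increase in CBF without naming a region, and the Background cites the same earlier study for the vasodilatory action of acetate-derived adenosine. If vasodilation is widespread, all six regions would rise together. The specified outputs contain no global value against which to judge whether any region rose more than the rest of the brain. Item 2 of IV.E raises vascular effects because BOLD mixes flow, volume and oxygenation, so the missing global value also weakens that safeguard.

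**Working it through.** **1. Reproduce the plan's figure.** Inputs from the power section: SD of the paired difference 0.085, n = 10, power 90%, Type I error 0.05. Sidedness is not stated; two-sided is assumed.

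Detectable difference = (z for 0.975 + z for 0.90) × SD / √n = (1.960 + 1.282) × 0.085 / √10 = 0.0871, which rounds to 0.09.

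The figure reproduces by normal approximation, and only in ratio units. With a t distribution it is 0.098 two-sided or 0.085 one-sided; with 2 degrees of freedom spent on covariates it is 0.102 two-sided. None of these variants changes the unit.

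**2. Set the benchmark beside the planned analyses.**

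| | Quantity | Unit | Cerebellar region | Global value |
|---|---|---|---|---|
| Power section | cortex/cerebellum | ratio | yes, as denominator | no |
| Regional paired t-tests | flow in six regions | mL/100g/min | no | no |
| Whole-brain ANCOVA | flow per voxel | maps in mL/100g/min; no global normalisation stated | no reference region | no |

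None of the planned CBF tests uses the quantity to which 0.054, 0.085 and 0.09 refer.

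**3. Show that the scales can disagree.** Let flow rise by 10% everywhere. Each region changes by +10%. The ratio becomes (1.10 × cortex) / (1.10 × cerebellum) = cortex / cerebellum, a change of 0, against 0.054 cited and 0.09 called detectable.

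**4. Try to convert 0.09 to absolute flow.** Change in cortical flow = (R + 0.09) × C × (1 + g) − R × C, where C is baseline cerebellar flow, R the baseline ratio and g the fractional change in cerebellar flow. The documents give none of these, so the ranges below are assumptions: C = 40 to 60 mL/100g/min, R = 0.9 to 1.1, g = −5% to +10%.

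- g = 0: 0.09 × 40 = 3.6, up to 0.09 × 60 = 5.4 mL/100g/min.
- Lowest (C = 40, R = 1.1, g = −5%): 1.19 × 38 − 44 = 1.2 mL/100g/min.
- Highest (C = 60, R = 1.1, g = +10%): 1.19 × 66 − 66 = 12.5 mL/100g/min.

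The same 0.09 spans about a tenfold range. The documents give nothing to narrow it, and no SD in mL/100g/min, so no detectable difference for the regional tests can be derived from them.

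**The case against.** The strongest reply is that little depends on the mismatch. The later study's CBF model (IV.F, CBF: ROI analyses) uses 12 measurements per participant, 6 regions × 2 treatments. The pilot collects flow in those same regions, so it supplies effect sizes and SDs on the scale the later study needs. Acetate and alcohol are measured with the same ASL method, and controls are randomised between branches, so comparing the two drugs does not depend on the outside ratio. The power figure uses 10 people while Study Design targets 15 usable controls per aim, so 0.09 does not set the sample size. The sentence on global effects sits among potential problems and is not a listed outcome. All of this stands.

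Two further points also stand. The uniform-rise example shows that the scales can diverge, not how far they would here; the earlier study's non-zero ratio change means its effect was not purely uniform. And the plan is silent on global normalisation in SPM12, which is not a statement that none is applied.

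None of this answers the narrower point. The plan asserts adequate power, and no planned CBF test uses the quantity that assertion describes. An uncorrected voxelwise map might show a widespread rise qualitatively, but it yields no global estimate, SD or interval. Even as a stated intention rather than an outcome, the study of global effects lacks a specified method.

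**Conclusion.** The mismatch is real and worth correcting. The power statement applies to none of the planned CBF tests, and the global effects have no specified estimate. From the specified outputs, a rise in all six regions could not be separated into global and regional change.

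A reader might infer more: that the pilot cannot size the larger study, cannot compare acetate with alcohol, or has lost the global information. The documents do not support this. Regional effect sizes and SDs are unaffected and the drug comparison is internal. A global mean could be derived from the same maps, as could the ratio if coverage allows. The gap is in the specified outputs, not in the data.

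The conclusion rests on the analysis text as written. The conversion range of 1.2 to 12.5 mL/100g/min is illustrative and depends wholly on the stated assumptions. Two facts remain unknown: whether the ASL slices reach the cerebellum, and how the earlier study defined cortex and cerebellum.

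A separate matter is that 0.09 exceeds the cited 0.054. Adequate power therefore does not follow even on the ratio scale, where a two-sided paired t-test for 0.054 has about 43% power at n = 10 and 63% at n = 15.

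**What to change.** **Power and Confidence Interval Width.** State that 0.054, 0.085 and 0.09 apply only to the cortex/cerebellum ratio, and that no power or detectable difference is available for absolute regional CBF. Withdraw the adequacy claim for the planned regional tests.

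**Regions-of-interest and CBF: ROI analyses.** Keep the six regions as planned. Add, as supporting summaries from the existing ASL maps:

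- mean grey-matter CBF per scan, with the paired change, its SD and a confidence interval, reported beside the six regional changes;
- if the acquired slices cover the cerebellum, the cortex/cerebellum ratio using the AAL atlas already named, with a note that its region definitions may differ from the earlier study's.

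This needs no change to the acquisition and does not promote the grey-matter mean above the regions. The cost is a few lines of text, a check of slice coverage, and one or two more descriptive CBF values to report.

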Statistical Analysis: We have three outcomes of interest: 1) CBF, 2) fMRI BOLD signal during decision-making, 3) behavioral measures. A bio-statistician employed part-time by the Department of Radiology will provide statistical support. The aim of this pilot study is simply to determine the feasibility of performing the experiment and to acquire the necessary data to calculate power needed for a larger study.

CBF: ROI analyses: For this feasibility pilot study, a paired t-test will be used to investigate the effect of acetate and the effect of alcohol separately. In an exploratory manner, drug x time interactions will be examined through descriptive and graphical analyses, though we acknowledge insufficient power to reject the null hypothesis of no interaction. Nevertheless, a noticeable difference in outcomes based on factors of drug or time could provide data to compute power for a larger, more powered study.

To provide context for this pilot, the statistical plan for the later, larger study is included: We will fit a general linear multivariate model with repeated measurements of CBF as the outcomes. Each participant will have 12 repeated measurements (6 ROIs x 2 treatments (acetate and placebo or alcohol and placebo)). Age and number of drinks per week will be included as covariates. MCMC imputation (Li, 1988) will be used to address missing data. A Chi-Muller test will be conducted (Chi and Muller, 2013) for the main effect of treatment (acetate versus placebo or alcohol versus placebo) at any ROI. Residual analysis will be used, and Box-Cox transformations will be considered to account for deviations from multivariate normality. An alpha spending approach will be used to handle multiple comparisons problems, by testing the overall hypothesis of no effect at any region at the $\alpha = 0.04$ level, and then, if we attain significance, testing the treatment effects at each ROI at the $\alpha = 0.01/6$ level. This yields a total Type I error for this aim of $0.05 = 0.04 + 6*(0.01/6)$.

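### The power paragraph concludes that power for alcohol is adequate, but its detectable difference (0.09) is 1.67 times the effect it cites (0.054); power for 0.054 is about 63% two-sided at the usable n of 15

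*Combined protocol and SAP*

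**What the plan says.** Section IV.F, Power and Confidence Interval Width, takes its inputs from one earlier study of blood flow before and after drinking, which reported a mean change in the cortex/cerebellum ratio "of 0.054 with standard deviation of the difference of 0.085". It says that the smallest difference detectable by 10 people "with 90% power and a Type 1 error of 0.05 is a difference of 0.09 (ratio of cortex/cerebellum"), using repeated measures ANCOVA. The next sentence draws the conclusion: "Therefore we should have adequate power to detect a difference with alcohol".

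Other sections supply the rest of the context:

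- **Hypothesis.** Aim 2(a) concerns the alcohol main effect: "compared to non-alcoholic jello shots, orally ingested alcohol jello shots will: a) increase CBF".
- **Test.** For the pilot ROI analysis of CBF, "a paired t-test will be used to investigate the effect of acetate and the effect of alcohol separately".
- **Sample size.** Section IV.C plans "to achieve a target of n=20 scanned for Aim 1 and n=20 scanned for Aim 2", with 15 usable controls for each aim. Session 1 assigns AUD participants to acetate only, so the alcohol arm consists of controls alone.
- **Outcome scale.** "Motion-corrected ASL CBF images (mL/100g/min) will be generated by the scanner software".
- **Admissions of low power.** Section IV.E makes one for sex effects. The ROI section makes one for drug-by-time interactions: "though we acknowledge insufficient power to reject the null hypothesis of no interaction". Neither covers the alcohol main effect.

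**The concern.** A smallest detectable difference supports a claim of adequate power only if it is no larger than the effect expected. Here it is larger, so the premises point away from the conclusion.

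The paragraph therefore claims power that its own figures do not give. The pilot is meant to estimate the effect and the N for a later study. A reader told that power was adequate could take a null alcohol result as evidence against an effect. With 15 usable controls, a true change of 0.054 would be missed 37% of the time two-sided (24% one-sided). With 20 it would be missed 23% of the time (14% one-sided).

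Two gaps lie in the same paragraph. Its heading names a confidence interval width, but none is given. Its figures are for a cortex/cerebellum ratio, whereas the planned outcome is ROI CBF from maps in mL/100g/min.

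**Working it through.** **Inputs.** Effect 0.054, SD of the difference 0.085, alpha 0.05, power 90% and n=10 come from the power paragraph. Usable n=15 and scanned n=20 come from section IV.C. The paired t-test comes from the ROI analysis section. Sidedness is not stated, so both versions are shown.

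**Reproducing the 0.09.** For a paired difference under the normal approximation, the detectable difference is SD × (z for alpha + z for power) / √n. Two-sided at n=10 this is 0.085 × (1.960 + 1.282) / √10 = 0.087, which rounds to 0.09. A one-sided t gives 0.085, or 0.088 with two degrees of freedom lost to covariates. A two-sided paired t gives 0.098. The stated figure is therefore consistent with two common methods.

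**Comparison with the cited effect.** 0.09 / 0.054 = 1.67. The standardised effect is 0.054 / 0.085 = 0.635.

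**Power for 0.054.** The noncentrality parameter is 0.635 × √n, which is 2.01, 2.46 and 2.84 at n=10, 15 and 20. Power is the probability that a noncentral t on n−1 degrees of freedom exceeds the critical value; the two-sided critical values are 2.262, 2.145 and 2.093.

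| | n=10 | n=15 | n=20 |
|---|---|---|---|
| Power for 0.054, two-sided t | 43.4% | 62.9% | 76.9% |
| Power for 0.054, one-sided t | 58.3% | 75.6% | 86.3% |
| Power for 0.054, two-sided normal approximation | 52.0% | 69.2% | 81.1% |
| Power for 0.054, one-sided normal approximation | 64.2% | 79.3% | 88.4% |
| Difference detectable at 90%, two-sided t | 0.098 | 0.077 | 0.065 |
| Difference detectable at 90%, one-sided t | 0.085 | 0.068 | 0.058 |
| Power for 0.09, two-sided t | 84.5% | 96.8% | 99.4% |

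A simulation of 400,000 trials at each n gave two-sided power for 0.054 of 43.6%, 63.0% and 77.0%.

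The planned sizes do give 90% power for 0.09. No row reaches 90% for 0.054, and every 90% detectable difference exceeds 0.054.

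**Loss of degrees of freedom.** Losing two for covariates, with no reduction in variance, gives 61.8% two-sided and 75.0% one-sided at n=15.

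**N needed for 0.054 (t-test).** For 80% power, 22 two-sided or 17 one-sided. For 90% power, 29 two-sided or 23 one-sided.

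**SD that would rescue the claim.** Two-sided 90% power for 0.054 needs an SD of 0.060 at n=15 (0.060 / 0.085 = 71% of the cited value) or 0.071 at n=20 (83%).

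**Confidence interval.** The 95% half-width at n=15 is 2.145 × 0.085 / √15 = 0.047, and 0.047 / 0.054 = 87% of the effect.

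**The case against.** The strongest reply has four parts.

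*The 63% is the least favourable reading at n=15.* It comes from a two-sided t, which does not itself reproduce 0.09. The methods that do reproduce it give 69% (two-sided normal) or 75–76% (one-sided t) at n=15, and 81% or 86% at n=20. Aim 2(a) is directional, so a one-sided test is arguable. This stands as a reason to report both versions. It does not rescue the sentence: the paired t is the test the plan names, and no variant reaches 90% at n=20 or fewer.

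*Adequate is not defined.* The 90% belongs to the detectable-difference sentence, and the plan does not say that adequacy means 90%. Against 80%, all 20 scans would pass under a one-sided test or the normal approximation, though not under the two-sided t (77%). That is fair, but the usable target of 15 falls below 80% in every variant tried.

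*Fifteen may be pessimistic for CBF.* The expected loss is attributed to head motion, and the only explicit motion exclusion is in the BOLD pre-processing. Section IV.C nevertheless sets 15 for Aim 2 as a whole, so this is a qualification only.

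*It is a feasibility pilot.* The plan says so repeatedly, and the sizes of 15 and 20 are not derived from this paragraph. This limits the weight of the point. It does not correct the sentence, because the plan nowhere disclaims power for the alcohol main effect.

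Covariate adjustment could in principle gain power, but the documents give no covariate correlation to support a gain.

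**Conclusion.** The concern holds. The conclusion about alcohol does not follow from the figures before it. At the cited SD, power for the cited effect is 63% two-sided or 76% one-sided with 15 usable controls, and 77% or 86% with 20. Ninety per cent power is reached at none of n=10, 15 or 20.

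This rests on a paired t-test at alpha 0.05, an SD of the difference of 0.085 that carries over to this study, and no variance reduction from covariates. It applies to the cortex/cerebellum ratio; the documents give no SD for ROI CBF in mL/100g/min, so power on the planned measure cannot be derived from them.

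The point should be fixed, but its weight is modest. It is an unsupported inference in one sentence, and no sample size, analysis or decision rule depends on it.

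**What to change.** Withdraw the concluding sentence and the n=10 figure, and replace them with text along these lines:

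> With 15 usable controls in the alcohol arm and the cited SD of 0.085, a paired t-test at alpha 0.05 has about 63% two-sided power (76% one-sided) for the cited 0.054 change in the cortex/cerebellum ratio. The 90%-power detectable difference is 0.077 (two-sided), and the expected 95% confidence interval half-width is 0.047. The pilot is not powered at 90% for the cited alcohol effect. These figures apply to the ratio measure and not to the planned ROI CBF in mL/100g/min, for which no SD is given here.

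This also supplies the interval width that the heading names. If only a minimal change is wanted, removing the concluding sentence corrects the error, but the interval width would still be missing.

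The cost is the rewording of one paragraph and a less favourable stated figure. It needs no extra participants and no change to design or analysis.
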